Appendix A. Outcome variables by ORCHID Use, Type, and Analysis Method.

Variable	ORCHID Use	Type	Analysis Method
Clinical status 14 days after randomization as assessed with a seven-category ordinal scale (COVID Ordinal Outcomes Scale on Study Day 15)	Primary Outcome	Ordinal	Proportional odds model accounting for pre-specified baseline covariates
Time to recovery	Secondary Outcome	Continuous	Proportional odds model accounting for pre-specified baseline covariates
All-location, all-cause 14-day mortality (Study Day 15)	Secondary Outcome	Binary	Logistic regression model accounting for pre-specified baseline covariates
All-location, all-cause 28-day mortality (Study Day 29)	Secondary Outcome	Binary	Logistic regression model accounting for pre-specified baseline covariates
Survival through 28 days (Study Day 29)	Secondary Outcome	Time to event	Proportional hazards regression model accounting for pre-specified baseline covariates
Hospital discharge through 28 days (Study Day 29)	Secondary Outcome	Time to event	Proportional hazards regression model accounting for pre-specified baseline covariates; death treated as a competing risk
COVID Ordinal Outcomes Scale on Study Day 3	Secondary Outcome	Ordinal	Proportional odds model accounting for pre-specified baseline covariates

COVID Ordinal Outcomes Scale on Study Day 8	Secondary Outcome	Ordinal	Proportional odds model accounting for pre-specified baseline covariates
COVID Ordinal Outcomes Scale on Study Day 29	Secondary Outcome	Ordinal	Proportional odds model accounting for pre-specified baseline covariates
Composite of death or receipt of ECMO through Day 28	Secondary Outcome	Binary	Logistic regression model accounting for pre-specified baseline covariates
Oxygen-free days through Day 28	Secondary Outcome	Ordinal	Proportional odds model accounting for pre-specified baseline covariates
Ventilator-free days through Day 28	Secondary Outcome	Ordinal	Proportional odds model accounting for pre-specified baseline covariates
Vasopressor-free days through Day 28	Secondary Outcome	Ordinal	Proportional odds model accounting for pre-specified baseline covariates
ICU-free days through Day 28	Secondary Outcome	Ordinal	Proportional odds model accounting for pre-specified baseline covariates
Hospital-free days through Day 28	Secondary Outcome	Ordinal	Proportional odds model accounting for pre-specified baseline covariates
Seizure	Safety Outcome	Binary	Simple logistic regression
Atrial arrhythmia	Safety Outcome	Binary	Simple logistic regression

Ventricular arrhythmia	Safety Outcome	Binary	Simple logistic regression
Cardiac arrest	Safety Outcome	Binary	Simple logistic regression
Elevation in aspartate aminotransferase or alanine aminotransferase above 2x upper limit of normal	Safety Outcome	Binary	Simple logistic regression
Acute pancreatitis	Safety Outcome	Binary	Simple logistic regression
Acute kidney injury	Safety Outcome	Binary	Simple logistic regression
Receipt of renal replacement therapy	Safety Outcome	Binary	Simple logistic regression
Symptomatic hypoglycemia	Safety Outcome	Binary	Simple logistic regression
Neutropenia	Safety Outcome	Binary	Simple logistic regression
Lymphopenia	Safety Outcome	Binary	Simple logistic regression
Anemia	Safety Outcome	Binary	Simple logistic regression
Thrombocytopenia	Safety Outcome	Binary	Simple logistic regression
Severe dermatologic reaction	Safety Outcome	Binary	Simple logistic regression

Appendix B: Outcome Definitions and Description of Derived Outcome Variables

Terminology for Outcome Intervals, Timing of Assessment, and Location of Assessment

The date and time of randomization represents “time zero” for all study assessments. The calendar day on which randomization occurred is referred to as “Study Day 1.” While patients are hospitalized during the index hospitalization, data are collected by in-person assessments and review of the medical record. Data are collected after hospital discharge via telephone calls at Day 8, Day 15, and Day 29. Long-term outcomes will be assessed in an ancillary study called ORCHID-Brain Outcomes and Psychological Disability (ORCHID-BUD). ORCHID BUD results will be reported separately and are not considered in this document.

The primary outcome, some secondary outcomes, and all safety outcomes were assessed until 28 days after randomization (Study Day 29) regardless of the patient’s location – referred to as “all-location outcomes.” Select secondary outcomes related to organ support (e.g., ventilator-free days) were only assessed until the patient’s discharge from the index hospitalization or 28 days after randomization (Study Day 29), whichever occurred first – referred to as “in-hospital outcomes.” All data collection ended on Study Day 29.

Definition of the Primary Outcome and SOFA score calculation

Primary Outcome

The primary outcome was patients’ clinical status 14 days after randomization (measured on Study Day 15) as assessed with the seven-category COVID Ordinal Outcome Scale:

1. Death
2. Hospitalized on invasive mechanical ventilation or extracorporeal membrane oxygenation
3. Hospitalized on non-invasive ventilation or high-flow nasal cannula
4. Hospitalized on supplemental oxygen
5. Hospitalized not on supplemental oxygen
6. Not hospitalized with limitation in activity
7. Not hospitalized without limitation in activity

If patients remained in the hospital, outcome assessment was performed by review of the electronic health records. For patients who were discharged prior to 14 days after randomization, study staff called patients or their surrogates to obtain patients’ clinical status (“all-location outcome”). To distinguish between category 6 (not hospitalized, but unable to perform normal activities) and category 7 (not hospitalized, able to perform normal activities), study personnel assessed the patient’s performance of “usual activities” with questions consistent with validated health status measures. An answer of “no problems doing my usual activities” resulted in assignment to category 7.

SOFA Score Calculation

The SOFA score at baseline (pre-randomization) was used as a co-variable in the regression models for the primary and secondary outcomes. The SOFA score was calculated using the definitions based on the Third International Consensus Definitions for Sepsis and Septic Shock (Sepsis-3).⁷ The SOFA score was calculated using data available in the 24 hours prior to randomization. We recorded the following data for SOFA score calculation: lowest PaO₂ and FIO₂ at the time of the lowest PaO₂ measurement; lowest SpO₂ and FIO₂ at the time of the lowest SpO₂ measurement; lowest platelet count; highest total bilirubin concentration; lowest Glasgow Coma Score; lowest mean arterial pressure; receipt and dose of inotropes/vasopressors, including dobutamine, dopamine, epinephrine, norepinephrine, phenylephrine, and vasopressin; highest creatinine; urine output; highest INR.

For calculation of the respiratory component of the SOFA score, if recorded, FiO₂ was used in the calculation of P:F or S:F ratio. If no FIO₂ was recorded, FiO₂ was estimated with the following equation: $0.21 + (\text{supplemental oxygen flow rate in liters/minute}) * 0.03$. If PaO₂ was recorded, the recorded PaO₂ value was used in the calculation of P:F ratio and respiratory SOFA score. If no PaO₂ value was recorded, respiratory SOFA score was classified by SpO₂ and SpO₂:FiO₂ ratio according to the table below based on the validated technique described by Pandharipande⁸:

Respiratory SOFA Score assignment based on SpO₂ and FIO₂ values when no PaO₂ is recorded	
Values	Respiratory SOFA Score Assignment
SpO ₂ ≥95% and FiO ₂ =0.21 (room air)	0
If SpO ₂ <95% or FiO ₂ >0.21, calculate the SpO ₂ :FiO ₂ ratio and assign respiratory SOFA score based on the thresholds below:	
SpO ₂ : FiO ₂ ≥357	1
SpO ₂ : FiO ₂ ≥214 and <357	2
SpO ₂ : FiO ₂ ≥89 and <214	3
SpO ₂ : FiO ₂ <89	4

When no P:F or S:F ratio is available, the respiratory SOFA score was imputed as the median observed value in the patients in the trial with non-missing values, consistent with the approach to missingness for other variables.

Definition of Secondary Outcomes

Time to Recovery

Recovery was defined as reaching category 5, 6, or 7 on the seven-category COVID Ordinal Outcome Scale. A patient could reach category 5, 6, or 7 on the seven-category COVID Ordinal Outcome Scale either by (a) being discharged from the hospital or by (b) being liberated from supplemental oxygen for the final time during the index hospitalization. Time to recovery was defined as the time between randomization and the first of either hospital discharge or liberation from supplemental

oxygen for the final time during the index hospitalization. Time to recovery was an “in-hospital outcome” and did not reflect information on receipt of supplemental oxygen, rehospitalization, or death after discharge from the index hospitalization.

For a patient who was not receiving supplemental oxygen at the time of randomization, and never received supplemental oxygen during the index hospitalization, the time to recovery was 0.0 days. For a patient who received supplemental oxygen at any time between randomization and discharge from the index hospitalization, but was not receiving supplemental oxygen at the time of discharge from the index hospitalization, the time to recovery was the time from randomization to the time of final receipt of supplemental oxygen during the index hospitalization. For a patient who was receiving supplemental oxygen at the time of discharge from the index hospitalization, the time to recovery was the time from randomization to the time of discharge from the index hospitalization. Patients who remained hospitalized and receiving supplemental oxygen 28 days after randomization were not considered to have experienced recovery. All patients who died prior to discharge from the index hospitalization were not considered to have experienced recovery. Patients who did not experience recovery were awarded a value for the outcome of time to recovery of 28.0 days.

All-location, all-cause 14-day mortality

Death between randomization and 14 days after randomization from any cause and in any location, including after discharge from the index hospitalization. Data on death were collected from the electronic health record during the hospitalization and then from telephone calls to the patient or surrogate after discharge on Study Day 8, 15 and 29.

All-location, all-cause 28-day mortality

Death between randomization and 28 days after randomization from any cause and in any location, including after discharge from the index hospitalization. Data on death were collected from the electronic health record during the hospitalization and then from telephone calls to the patient or surrogate after discharge on Study Day 8, 15 and 29.

Survival through 28 days

Dead versus survived will be recorded between randomization and 28 days following randomization using in-hospital data and follow-up calls post-discharge on Study Day 8, 15, and 29. Using these data, survival curves through 28 days following randomization will be constructed.

Hospital discharge through 28 days

Time of hospital discharge from the index hospitalization for COVID-19 will be recorded. Using these data, time to hospital discharge curves through 28 days following randomization will be constructed. Death will be treated as a competing risk.

COVID Ordinal Outcomes Scale on Study Day 3

Clinical status 2 days after randomization (measured on Study Day 3) as assessed with the seven-category COVID Ordinal Outcome Scale, as described in the section on the *Primary Outcome*. Data on clinical status were collected from the electronic health record during the hospitalization. Patients discharge prior to Study Day 3 will have the Day 3 COVID Ordinal Outcome Scale coded as level 6 (not hospitalized with limitation in activity).

COVID Ordinal Outcomes Scale on Study Day 8

Clinical status 7 days after randomization (measured on Study Day 8) as assessed with the seven-category COVID Ordinal Outcome Scale, as described in the section on the *Primary Outcome*. Data on clinical status were collected from the electronic health record during the hospitalization and then from telephone calls to the patient or surrogate after discharge from the index hospitalization (“all-location outcome”).

COVID Ordinal Outcomes Scale on Study Day 29

Clinical status 28 days after randomization (measured on Study Day 29) as assessed with the seven-category COVID Ordinal Outcome Scale, as described in the section on the *Primary Outcome*. Data on clinical status were collected from the electronic health record during the hospitalization and then from telephone calls to the patient or surrogate after discharge from the index hospitalization (“all-location outcome”). Missing data for the COVID Ordinal Outcomes Scale on Day 29 will be handled in the same fashion as describe for the primary outcome.

Composite of death or receipt of ECMO through Day 28

Death or receipt of extra-corporeal membrane oxygenation (ECMO) between randomization and discharge from the index hospitalization or 28 days after randomization, whichever occurs first (“in-hospital outcome”). Patients who were receiving ECMO at the time of randomization could qualify for this outcome by experiencing death, but not by continuing to receive ECMO.

Days Free of Support

For all outcomes related to days alive and free from a supportive therapy, “-free days” were calculated as the number of whole calendar days from 00:00 on the day of randomization (Study Day 1) to 23:59 on Study Day 28. The day of randomization contributed to the count of “-free days”. Days between randomization and the first receipt of the supportive therapy and days following the last day of the support therapy both counted toward the total number of “-free days”. Days alive and free of the supportive therapy that occurred between periods receiving support did not count toward “-free days”.

Information on organ support therapies (oxygen, ventilation, vasopressors, ICU care) were collected during the index hospitalization (“in-hospital data”) while death was collected both in-hospital and out-of-hospital to Study Day 29 (“all-location data”). Thus, patients who died at any time before Study Day 29 were coded as having zero-free days.

Oxygen-free days through Day 28

For calculation of oxygen-free days, supplemental oxygen was defined as oxygen administered by nasal cannula, face mask, high-flow nasal cannula, non-invasive ventilation, or invasive ventilation. Positive airway pressure (CPAP, BiPAP) provided solely at night as treatment for sleep-disordered breathing (e.g. obstructive sleep apnea) was not considered supplemental oxygen. Oxygen-free days were calculated as the number of whole calendar days alive and not receiving supplemental oxygen between randomization and study day 29. Patients who died before Day 29 received a value of 0. If a patient survived through study day 29 and never received supplemental oxygen, the number of oxygen-free days was 28. If a patient received supplemental oxygen and survived through study day 28, the number of oxygen free-days was calculated as 28 minus the number of calendar days from the first day on which the patient received supplemental oxygen until the last day on which the patient received supplemental oxygen. Days on which the patient did not receive supplemental oxygen that occurred between days on which the patient received supplemental oxygen did not count towards the number of oxygen free days. Data on oxygen use were censored at hospital discharge and the last observed status was carried forward (“in-hospital outcome”). That is, if the patient was receiving supplement oxygen at hospital discharge, the analysis assumed they continued to receive supplemental oxygen through Study Day 29. If the patient was not receiving supplemental oxygen at hospital discharge, the analysis assumed the patient continued not to receive supplemental oxygen through Study Day 29.

Ventilator-free days to Day 28

Ventilator-free days to day 28 was defined as the number of whole calendar days alive and breathing without invasive mechanical ventilation from 00:00 on the day of randomization through Study Day 29. Patients who died before Study Day 29 received a value of 0. If a patient survived to the first of discharge or Study Day 29 and never received invasive mechanical ventilation, the number of VFDs was 28. If a patient received invasive mechanical ventilation and survived to the first of hospital discharge or Study Day 28, the number of VFDs was calculated as 28 minus the number of calendar days from the first day on which the patient received invasive mechanical ventilation until the last day on which the patient received invasive mechanical ventilation. Days on which the patient did not receive invasive mechanical ventilation that occurred between days on which the patient received mechanical ventilation did not count towards the number of VFDs. Data on ventilation were censored at hospital discharge and the last observed status was carried forward (“in-hospital outcome”). That is, if the patient was receiving invasive mechanical ventilation at hospital discharge, the analysis assumed they continued to receive invasive mechanical ventilation through Study Day 29. If the patient was not receiving invasive mechanical ventilation at hospital discharge, the analysis assumed the patient continued not to receive invasive mechanical ventilation through Study Day 29.

Vasopressor-free days to Day 28

For vasopressor-free days, a day on which a patient received any of the following medications via intravenous drip or push at any dose was considered a day receiving vasopressors: norepinephrine, epinephrine, vasopressin, phenylephrine, angiotensin II, dobutamine, dopamine, or milrinone. Vasopressor-free days to Day 28 was calculated as the number of whole calendar days alive and not receiving intravenous vasopressors or inotropes from 00:00 on the day of randomization through study day 29. Patients who died before Study Day 29 receive a value of 0. If a patient survived to Study Day 29 and never received intravenous vasopressors or inotropes, the number of vasopressor-free days was 28. If a patient received intravenous vasopressors or inotropes and survived to the first of discharge or Study Day 29, the number of vasopressor-free days was calculated as 28 minus the number of calendar days from the first day on which the patient received vasopressors or inotropes until the last day on which the patient received vasopressors or inotropes. Days on which the patient did not receive vasopressors or inotropes that occurred between days on which the patient received vasopressors or inotropes did not count towards the number of vasopressor-free days. Data on vasopressor use was censored at hospital discharge and the last observed status was carried forward (“in-hospital outcome”). That is, if the patient was known to be receiving vasopressors or inotropes at hospital discharge, the analysis assumed they continued to receive vasopressors or inotropes through Study Day 29. If the patient was not receiving vasopressors or inotropes at hospital discharge, the analysis assumed the patient continued not to receive vasopressors or inotropes through Study Day 29.

ICU-free days to Day 28

Intensive care unit-free days (ICU-free days) to day 28 was defined as the number of whole calendar days alive and not admitted to an intensive care unit from 00:00 on the day of randomization through Study Day 29. Patients who died before Study Day 29 received a value of 0. If a patient survived to the first of discharge or Study Day 29 and was never admitted to an ICU, the number of ICU-free days was 28. If a patient was admitted to an ICU and survived to the first of discharge or Study Day 28, the number of ICU-free days was calculated as 28 minus the number of calendar days from the first ICU admission to final ICU discharge. Days on which the patient was not admitted to an ICU that occurred between days on which the patient was admitted to an ICU did not count towards the number of ICU-free days. Data on ICU use was censored at hospital discharge and the last observed status was carried forward (“in-hospital outcome”). That is, the analysis assumed that a patient who was discharged from the index hospitalization was not readmitted to an ICU between hospital discharge and Study Day 29.

Hospital-free days to Day 28

Hospital-free days to Day 28 was defined as the number of whole calendar days on which the patient was alive and not in the hospital from 00:00 on the day of randomization through Study Day 29. Patients who died before Study Day 29 received a value of 0. If a patient remained in the hospital during the index hospitalization through Study Day 29, the number of hospital-free days was 0. For patients

discharged from the index hospitalization prior to Study Day 28, the number of hospital-free days was calculated as 28 minus the duration of the index hospitalization in calendar days. Information readmissions occurring after discharge from the index hospitalization did not contribute to the calculation of the hospital-free days outcome.

Definition of Safety Outcomes (“all-location outcomes”)

1. Seizure – Between randomization and Study Day 29, as documented by treating clinicians in the electronic health record or reported by patient or surrogate on follow up telephone call.
2. Atrial arrhythmia - Between randomization and Study Day 29, as documented in the electronic health record or reported by patient or surrogate on follow up telephone call.
3. Ventricular arrhythmia - ventricular tachyarrhythmia (ventricular fibrillation or ventricular tachycardia) treated with a medication or electrical cardioversion or debrillation between randomization and Study Day 29, as documented in the electronic health record or reported by patient or surrogate on follow up telephone call.
4. Cardiac arrest - Between randomization and Study Day 29, as documented in the electronic health record or reported by patient or surrogate on follow up telephone call. Does not include expected cardiac arrests occurring as a part of the dying process for patients on comfort measures.
5. Elevation in aspartate or alanine aminotransferase to twice the upper limit of normal – Between randomization and Study Day 29, as documented in the electronic health record or reported by patient or surrogate on follow up telephone call.
6. Acute Pancreatitis – Clinically-obtained lipase level above the local upper limit of normal between randomization and day 29.
7. Acute Kidney Injury – Stage II or greater acute kidney injury by Kidney Disease Improving Global Outcomes (KDIGO) Criteria between randomization and day 29, defined as any of the following:
 - a. Creatinine at least 2.0 times the baseline value
 - b. Increase in serum creatinine above 4.0 mg/dl
 - c. Urine output less than 0.5 ml/kg/h for at least 12 hours
 - d. Initiation of new renal replacement therapy
8. Receipt of renal replacement therapy – Between randomization and Study Day 29, as documented by treating clinicians in the electronic health record or reported by patient or surrogate on follow up telephone call.
9. Symptomatic hypoglycemia – Between randomization and Study Day 29, as documented by treating clinicians in the electronic health record or reported by patient or surrogate on follow up telephone call.
10. Neutropenia – Clinically-obtained absolute neutrophil count < 1000 (cells/mm³) between randomization and Study Day 29
11. Lymphopenia – Clinically obtained absolute lymphocyte count < 1000 (cells/mm³) between randomization and Study Day 29.
12. Anemia – Clinically-obtained hemoglobin < 12.0 g/dL between randomization and Study Day 29.

13. Thrombocytopenia – Clinically-obtained platelet count < 50 (cell/mm³; in thousands) between randomization and Study Day 29.
14. Severe dermatologic reaction – Between randomization and Study Day 29, as documented by treating clinicians in the electronic health record or reported by patient or surrogate on follow up telephone call.

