6. DATA COLLECTION

Given the infectious risk from COVID-19 and potential shortages of personal protective equipment (PPE), we will minimize face-to-face contact between patients and non-clinical staff. Additionally, minimizing research activities and conducting the trial in a pragmatic manner will increase the ability to complete the trial in the face of strained clinical and research resources during the COVID-19 pandemic. We will emphasize data that can be collected from the electronic health record, radiographs obtained as part of routine clinical care, and assessments that can be completed over the telephone as needed.

Biological specimens will not be collected as part of this trial. To further elucidate the pathophysiology of COVID-19 and the effects of hydroxychloroquine, we encourage ancillary studies and co-enrollment in observational studies that collect biological specimens and more detailed data.

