6.2 Assessments between Hospital Presentation and Hospital Discharge

- Specimen type, date, and result of SARS-CoV-2 testing conducted clinically
- Specimen type, date, and result of viral testing conducted clinically
- Specimen type, date, and result of bacterial testing conducted clinically
- Date and time of study drug administration and reason for missed doses
- COVID Ordinal Outcomes Scale on Days 2, 3, 4, 5, 8, 15, and 29
- SOFA on Day 3
- S/F ratio on Day 3
- Receipt of open label antivirals between randomization and hospital discharge: chloroquine, hydroxychloroquine, remdesivir, lopinavir/ritonavir, other
- Receipt of open label immunomodulators between randomization and hospital discharge: corticosteroids, tocilizumab, sarilumab, interferon β , other
- Receipt of convalescent plasma between hospital presentation and enrollment
- Receipt of azithromycin and other antibiotics between randomization and Day 8
- Clinically diagnosed deep vein thrombosis (DVT) or pulmonary embolism (PE) between hospital presentation and hospital discharge.
- Date and time of first receipt of supplemental oxygen (if applicable)
- Date and time of final receipt of supplemental oxygen (if applicable)
- Date and time of first receipt of high flow nasal cannula (if applicable)

- Date and time of final receipt of high flow nasal cannula (if applicable)
- Date and time of first receipt of non-invasive ventilation (if applicable)
- Date and time of final receipt of non-invasive ventilation (if applicable)
- Date and time of first receipt of invasive mechanical ventilation (if applicable)
- Date and time of final receipt of invasive mechanical ventilation (if applicable)
- Date and time of first receipt of extracorporeal membrane oxygenation (if applicable)
- Date and time of final receipt of extracorporeal membrane oxygenation (if applicable)
- Date and time of first receipt of vasopressors (if applicable)
- Date and time of final receipt of vasopressor (if applicable)
- Date and time of first meeting the Berlin Diagnostic Criteria for ARDS³³ (if applicable)
- Date and time of first ICU admission (if applicable)
- Date and time of final ICU discharge (if applicable)
- Date and time of hospital discharge (if applicable)
- Date of death (if applicable)

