- Safety Outcomes: seizure, atrial or ventricular arrhythmia, cardiomyopathy, cardiac arrest, aspartate aminotransferase or alanine aminotransferase levels that are greater than twice the local upper limit of normal, acute pancreatitis (defined by a clinically obtained lipase level above the local upper limit of normal), stage II or greater acute kidney injury according to KDIGO criteria³⁴, receipt of new renal replacement therapy, symptomatic hypoglycemia, neutropenia, lymphopenia, anemia, thrombocytopenia, or severe dermatologic reaction (e.g., Steven's Johnson Syndrome)
- Patient destination at discharge

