6.3 Assessments following Hospital Discharge

6.3.1 Acute Care Follow-up

For participants discharged from the study hospital prior to the Day 8, Day 15 or Day 29 assessment, we will perform these assessments via telephone follow-up. The Day 8 call window will be Day 8 through 14. The Day 15 call window will be Day 15 through 22. The Day 29 call window will be Day 29 through 36. During these telephone calls, we will interview the patient, LAR, or facility staff to assess:

- Number and reason for missed doses of study drug (only for those discharged prior to completing study drug)
- Date of death (if applicable)
- ED visits, hospital readmissions, and use of supplemental oxygen after hospital discharge
- Non-laboratory safety outcomes after hospital discharge and adverse events
- Symptoms of acute respiratory infection
- COVID Ordinal Outcomes Scale

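### SAP Appendix B claims any-location assessment to Day 29 for all safety outcomes, but five of the fourteen have no planned data source after discharge

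*SAP*

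**What the plan says.** SAP Appendix B, under the terminology for outcome intervals, says that "all safety outcomes were assessed until 28 days after randomization (Study Day 29", and that this holds in any location. The heading over the safety definitions repeats the all-location label. The same paragraphs give the source of data once a patient has gone home: "Data are collected after hospital discharge via telephone calls at Day 8, Day 15, and Day 29".

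Protocol 6.3.1 sets the content of those calls. Its safety item reads "Non-laboratory safety outcomes after hospital discharge and adverse events". The laboratory safety outcomes appear instead in protocol 6.2, titled "Assessments between Hospital Presentation and Hospital Discharge", for example "acute pancreatitis (defined by a clinically obtained lipase level above the local upper limit of normal". Protocol section 6 adds "Biological specimens will not be collected as part of this trial", so every laboratory value comes from routine care.

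The SAP definitions follow suit: neutropenia is a "Clinically-obtained absolute neutrophil count < 1000" between randomization and Study Day 29. The other three blood-count outcomes and pancreatitis are defined in the same way.

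SAP Appendix A and section 7.5 treat each safety outcome as binary and analyze it by unadjusted logistic regression. SAP 7.1 makes all enrolled patients the default population. SAP 7.8 gives missing-data rules for the primary outcome, covariates and secondary outcomes, and none for safety outcomes.

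**The concern.** The SAP claims follow-up that the data collection cannot deliver. A laboratory abnormality that arises at home is not asked about on the calls, and no sample is scheduled that would reveal it. How long a patient is observed for these outcomes therefore depends on length of stay, and within the stay on how often clinicians order tests.

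Two things are at stake. First, a report based on this wording would present 28-day, any-location rates of laboratory toxicity that were in fact in-hospital rates over varying periods. Second, if one arm goes home sooner, that arm has less time in which an abnormality can be found.

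The SAP already recognizes this limit elsewhere. Section 7.5 says that organ-support data stop at discharge from the index hospitalization, and Appendix B defines an in-hospital category for those outcomes. The laboratory safety outcomes share the limit but carry the opposite label.

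**Working it through.** The plan states no figure on this point, so there is nothing to reproduce. The check is a comparison of texts, followed by arithmetic for scale.

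**1. Source after discharge for each of the fourteen outcomes (SAP Appendices A and B against protocol 6.2 and 6.3.1)**

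| Outcomes | Planned source after discharge | Count |
|---|---|---|
| Seizure, atrial arrhythmia, ventricular arrhythmia, cardiac arrest, renal replacement therapy, symptomatic hypoglycemia, severe dermatologic reaction | Telephone report, consistent with protocol 6.3.1 | 7 |
| Pancreatitis (lipase), neutropenia, lymphopenia, anemia, thrombocytopenia | None stated | 5 |
| AST/ALT elevation | Telephone report in the SAP, in conflict with the non-laboratory limit in protocol 6.3.1 | 1 |
| Acute kidney injury | Only the renal replacement criterion; creatinine and urine output have no source at home | 1 |

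The all-location label is supported for seven, unsupported for five, contested for one and partly supported for one.

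**2. How unobserved days enter the analysis**

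The outcome is yes or no, the denominator is everyone enrolled, and there is no time-at-risk term and no rule for a patient without a result. The natural reading is that days without observation contribute no event. No sentence says this.

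**3. How many patients**

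Inputs: 510 patients. Table 1 in protocol 7.1 has 60.8% discharged at Day 15. The text above that table gives 22.9% still in hospital where the table gives 21.9%; with the text figure, 100 − 11.5 − 5.8 − 22.9 = 59.8% discharged.

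- 0.598 × 510 = 305 and 0.608 × 510 = 310 patients.
- Each has at least 28 − 14 = 14 days without planned laboratory collection.
- Share of the full window: 305 × 14 = 4,270, or 310.08 × 14 = 4,341, out of 510 × 28 = 14,280 patient-days. That is 29.9% to 30.4%. The denominator gives every patient 28 days, including those who die.

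**4. Illustration with no true safety difference**

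Assumptions, not document figures: constant hazard, true 28-day risk r from 5% to 40%, discharged patients observed for t = 14 or 7 days, all others for 28 days. With d the share discharged:

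observed risk = d × [1 − (1 − r)^(t/28)] + (1 − d) × r

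Example with r = 0.10, t = 14, d = 0.608: 1 − 0.9^0.5 = 0.0513, and 0.608 × 0.0513 + 0.392 × 0.10 = 0.0704. The missed share is 1 − 0.0704/0.10 = 29.6%. With the same d in both arms, the odds ratio is 1.00.

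To see what unequal discharge could do, apply the plan's design odds ratio of 1.8 to discharge: odds 0.608/0.392 × 1.8 = 2.79, so d = 73.6% on hydroxychloroquine against 60.8% on placebo.

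| Days observed if discharged | Events missed at d = 60.8% | Apparent OR, equal discharge | Apparent OR, 73.6% vs 60.8% discharged |
|---|---|---|---|
| 14 | 26.5% to 30.0% | 1.00 | 0.895 to 0.907 |
| 7 | 42.6% to 45.3% | 1.00 | 0.806 to 0.821 |

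**The case against.** The best defense is that this is a labelling slip with little consequence. Assignment is randomized and blinded, so testing is not driven by knowledge of the arm. Dosing lasts five days, so the last 14 days of the window fall after treatment. Calls record readmissions, emergency visits and adverse events, and protocol 11.2 keeps events judged related to study drug or procedures reportable after discharge, so a toxicity that makes a patient ill would not necessarily be lost. The 60.8% is a planning approximation from an earlier trial in another population, and it counts discharges, not missed events.

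Most of this stands, and it is why the point is minor. It does not rescue the sentence in Appendix B: a laboratory value that causes no illness still has no planned route into the data. Protocol 4.1 also sends patients home with study drug, so a patient discharged before Day 5 can have dosing days without laboratory observation. That section mentions collecting safety outcomes by telephone for such patients, but 6.3.1 specifies the non-laboratory ones.

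A reader might infer three stronger things.

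- *That the plan codes discharged patients as event-free.* It is the likely result, but the documents leave the coding unstated, and a patient whose event was recorded before discharge would count as having it.
- *That all seven outcomes resting on laboratory values are unobservable at home.* The SAP names a telephone source for AST/ALT, and renal replacement therapy makes some kidney injury reportable.
- *That the comparison between arms is confounded.* Length of stay is a consequence of randomization, not a baseline confounder. With equal discharge and testing the odds ratio stays at 1.00; the values below 1 above need an assumed effect on discharge.

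**Conclusion.** The contradiction is on the page. The SAP attributes to all safety outcomes an ascertainment that the protocol's data collection does not provide for five of fourteen, provides only in part for acute kidney injury, and leaves in conflict for AST/ALT. On the planning figures, about 305 to 310 of 510 patients would lack planned laboratory collection for at least half of the 28-day window.

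The firm consequence is under-counting and a 28-day, any-location claim without support. Bias between arms is conditional on discharge or testing differing by arm, and neither document shows that it does. The 60.8% planning share and the assumed risks and observed days give the order of size only. This is a minor point that affects how far the laboratory safety results can be interpreted. It does not touch the primary analysis.

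**What to change.** In SAP Appendix B:

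- Relabel the laboratory-based safety outcomes as in-hospital outcomes, from randomization to discharge or Day 29, whichever is first. Keep renal replacement therapy and the other clinical events asked about on the calls as all-location.
- Reconcile the telephone source for AST/ALT with protocol 6.3.1.
- State how a patient with no post-randomization result is coded.
- Keep the all-enrolled analysis as the main one. Beside it, report by arm the number of patients tested and the observed days for each laboratory outcome.

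An analysis restricted to tested patients may be shown as a supplement. It should not replace the main one: being tested is a post-randomization event, the restriction departs from the population in SAP 7.1, and it could drop kidney injury identified by urine output or renal replacement therapy.

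Relabelling does not remove the dependence on length of stay. It makes it explicit, and the table of observed days lets the reader judge whether it differs by arm. The cost is a change of wording, one extra table and a narrower safety claim. No new data collection is needed.
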